6 CONSENT

Eligible patients have already given consent for participation in the TARGIT-A trial. We shall seek consent from each patient for direct patient contact, and collection of information from national records such as the Office for National Statistics (ONS).

7 ELIGIBILITY CRITERIA

7.1 Inclusion Criteria

All patients who participated in the TARGIT-A trial.

7.2 Exclusion Criteria

Any patient who has withdrawn consent for further follow-up, or died.

8 RECRUITMENT

All eligible patients who participated in the TARGIT-A trial (from March 2000 to June 2012) will be included. Patients will be identified from the TARGIT-A database, and lists of eligible patients will be sent to Principal Investigators at each site. Each patient will be given an information sheet and consent form, either when they attend clinic, or by post. Completed consent forms will be returned to the Trials Office, who will then contact patients directly for subsequent follow-up.

9 STATISTICAL METHODS

This protocol only relates to continuing collection of follow up information from patients already in the TARGIT-A trial. Formal statistical analysis will be performed as per the original TARGIT-A trial. In brief, analysis will be performed as per the submitted Statistical Analysis Plan (SAP) that has been signed off by the Chair of the DMC ([name]). As usual, any modifications of the SAP, based on new information such as data from other trials and biological insights, will be finalized and signed off BEFORE unblinding of the database. The current plan is to analyse as by pre-pathology and post-pathology strata as well as subgroup analysis as per hormone receptor status and hormone therapy. Multivariate analysis will also be performed for assessing the predictive value of other tumour and patient factors such as age, tumour size, grade, lymph node status, margins, lymphovascular invasion, time since randomization, etc.

10 PATIENT AND PUBLIC INVOLVEMENT (PPI)

A patient sits on the Trial Steering Committee and has been involved in discussions about the management of the research, analysis of results and dissemination of findings.

In addition, a minimum of one patient focus group meeting per annum will be held. Items to be discussed include responding to feedback from patient-completed questionnaires, informing the group of study progress, and addressing more general questions. At the end of recruitment, the patient focus group meeting will be mainly concerned with the dissemination plan.

11 FUNDING AND SUPPLY OF EQUIPMENT

The study funding has been reviewed by the UCL/UCLH Research Office, and deemed sufficient to cover the requirements of the study. NHS costs will be supported via UCLH and/or the Local Clinical Research Network.

Extended follow up of the TARGIT-A trial - Protocol

IRAS No: 236431

The research costs for the study have been supported by the NIHR HTA programme.

12 DATA HANDLING AND MANAGEMENT

The clinical trials unit (SITU) will send to each Principal Investigator a list of patients who meet the eligibility criteria as per information held on the database (alive, not withdrawn consent). The PI will review the list to ensure the information is up-to-date.

The PI will send the approved letter (on local letterhead) to each patient, together with the participant information leaflet, consent form, contact details form, and follow-up (questionnaire) form. If the patient has any questions, she can telephone the office of the PI (contact details will be provided), or have a face-to-face discussion at her next clinic visit.

If the patient consents to take part in the study, she must complete the consent form, contact details form, and follow-up (questionnaire) form. These should be sent to SITU by post in the pre-paid envelope provided. One copy of the consent form will be returned to the patient, one copy will be sent to the PI, and the original will remain in SITU.

If the patient explicitly states that she refuses to participate, no further contact will be made. If the patient does not reply, the PI will be asked to send a reminder to the patient. If no contact is made after three attempts, no further contact will be made.

Patients who have consented to be in the study will be "flagged" with administrative databases (such as ONS and the Cancer Registry). In addition, the patient will be contacted annually directly by SITU and asked to update the contact details form (if necessary), complete a follow-up (questionnaire) form, and return by post in the pre-paid envelope provided. Patients can refuse consent at any time by contacting either SITU or the PI, in which case no further contact will be made.

All data obtained will be held securely in UCL. Patient identifiers (such as name, address, etc.) will be held on a separate Data Safe Haven which has been certified to the ISO27001 information security standard and conforms to NHS Digital's Information Governance Toolkit. This has been built using a walled garden approach, where the data is stored, processed and managed within the security of the system, avoiding the complexity of assured end point encryption. A file transfer mechanism enables information to be transferred into the walled garden simply and securely.

Long term arrangements will be as per the sponsors SOP. On publication of the final analysis and closure of all sites, the main REC (HRA) will be notified using the appropriate forms. All essential documentation, CRFs and electronic records will be catalogued and boxed up. All duplicates and non essential documentation will be confidentially destroyed. These boxes will be held off site within UCLs commercial storage, provided by Iron Mountain. These data will be held for 20 years, at the end of which they will also be confidentially destroyed.

The principal investigator at each participating site agrees to archive his/her respective site's study documents for 20 years and in line with all relevant legal and statuary requirements.

13 MATERIAL/SAMPLE STORAGE

No tissue or samples will be collected from patients as part of this study.

14 PEER AND REGULATORY REVIEW

The Sponsor considers the procedure for obtaining funding from the NIHR HTA programme to be of sufficient rigour and independence to be considered an adequate peer review.

15 ASSESSMENT AND MANAGEMENT OF RISK

There is a risk that some patients might feel upset at being reminded about their diagnosis and treatment for breast cancer. The initial letter from the treating hospital will include contact details of the team and breast care nurses for easy access.

16 RECORDING AND REPORTING OF EVENTS AND INCIDENT

As the last treatment occurred more than 5 years ago, this section (16) will be relevant in the rare case of any adverse event that is being reported retrospectively, or a rare event that occurs in the course of longer follow up that may be attributed to radiation therapy (e.g. lung cancer, oesophageal cancer, angiosarcoma, ischaemic heart disease, rib facture, etc.).

16.1 Definitions of Adverse Events

| Term | Definition | |
|------------------------------|---------------------------------------------------------------------------------------------------------------------------------------------------------------------------------------------------|--|
| Adverse Event (AE) | Any untoward medical occurrence in a patient or study participant which does not necessarily have a causal relationship with the procedure involved. | |
| Serious Adverse Event (SAE). | Any adverse event that: results in death, is life-threatening*, requires hospitalisation or prolongation of existing hospitalisation**, | |
| | results in persistent or significant disability or incapacity, or consists of a congenital anomaly or birth defect this refers to an event in which the participant was at risk of death | |

^{*}A life- threatening event, this refers to an event in which the participant was at risk of death at the time of the event; it does not refer to an event which hypothetically might have caused death if it were more severe.

16.2 Assessments of Adverse Events

Each adverse event will be assessed for severity, causality, seriousness and expectedness as described below.

16.2.1 Severity

The generic categories below are given for use as a guide.

| Category | Definition |
|----------|------------|
| | |

Extended follow up of the TARGIT-A trial - Protocol

IRAS No: 236431

^{**} Hospitalisation is defined as an in-patient admission, regardless of length of stay.

Hospitalisation for pre-existing conditions, including elective procedures do not constitute an SAE.

| Mild | The adverse event does not interfere with the participant's daily routine, and does not require further procedure; it causes slight discomfort |
|----------|--------------------------------------------------------------------------------------------------------------------------------------------------------------------------|
| Moderate | The adverse event interferes with some aspects of the participant's routine, or requires further procedure, but is not damaging to health; it causes moderate discomfort |
| Severe | The adverse event results in alteration, discomfort or disability which is clearly damaging to health |

16.2.2 Causality

The assessment of relationship of adverse events to the procedure is a clinical decision based on all available information at the time of the completion of the case report form.

If a differentiated causality assessment which includes other factors in the study is deemed appropriate, please add/amend the following wording to specify:

It is of particular importance in this study to capture events related to the treatment. The assessment of relationship of an adverse event to this/these additional safety issue(s) will also be carried out as part of the study.

The following categories will be used to define the causality of the adverse event:

| Category | Definition | |
|----------------|----------------------------------------------------------------------------------------------------------------------------------------------------------------------------------------------------------------------------------------------------------------------------------------------------------|--|
| Definitely: | There is clear evidence to suggest a causal relationship, and other possible contributing factors can be ruled out. | |
| Probably: | There is evidence to suggest a causal relationship, and the influence of other factors is unlikely | |
| Possibly | There is some evidence to suggest a causal relationship (e.g. the event occurred within a reasonable time after administration of the study procedure). However, the influence of other factors may have contributed to the event (e.g. the participant's clinical condition, other concomitant events). | |
| Unlikely | There is little evidence to suggest there is a causal relationship (e.g. the event did not occur within a reasonable time after administration of the study procedure). There is another reasonable explanation for the event (e.g. the participant's clinical condition). | |
| Not related | There is no evidence of any causal relationship. | |
| Not Assessable | Unable to assess on information available. | |

16.2.3 Expectedness

| Category | Definition |
|------------|----------------------------------------------------------------------------------------------------------------------------|
| Expected | An adverse event which is consistent with the information about the procedure defined in the TARGIT A Trial protocol. |
| Unexpected | An adverse event which is not consistent with the information about the procedure defined in the TARGIT A Trial protocol*. |

^{*} this includes listed events that are more frequently reported or more severe than previously reported

16.3 Recording adverse events

All adverse events will be recorded in the medical records in the first instance.

All adverse events will be recorded with clinical symptoms and accompanied with a simple, brief description of the event, including dates as appropriate.

All adverse events will be recorded in the CRF until the participant completes the study.

16.4 Procedures for recording and reporting Serious Adverse Events

All serious adverse events will be recorded in the medical records and the CRF. The sponsors AE log is used to collate SAEs and AEs so that the CI can review all in one place for trend analysis. This data will be collated on a database throughout the study, from which a line listing of the SAEs can be extracted for review; therefore an AE log will not be required.

[figure not shown]
All SAEs (except those specified in section 16.5 as not requiring reporting to the Sponsor) must be recorded on a serious adverse event (SAE) form. The CI/PI or designated individual will complete an SAE form and the form will be preferably emailed to the Sponsor within 5 working days of becoming aware of the event. The Chief or Principal Investigator will respond to any SAE queries raised by the sponsor as soon as possible.

Where the event is unexpected and thought to be related to the procedure this must be reported by the Investigator to the Health Research Authority within 15 days.

Completed forms for unexpected SAES must be sent within 5 working days of becoming aware of the event to the Sponsor

Email forms to [contact]

Flow Chart for SAE reporting

16.5 Serious Adverse Events that do not require reporting

As treatment occurred more than 5 years ago, the only reportable adverse events are those that that occur in the course of longer follow up that may be attributed to radiation therapy (e.g. lung cancer, oesophageal cancer, angiosarcoma, ischaemic heart disease, rib facture, etc.).

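### Section 16 leaves it unclear whether late adverse events not attributed to radiation are recorded in the CRF at all

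*Protocol*

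**What the plan says.** The opening paragraph of section 16 sets the scope of the whole section in two limbs. The first has no attribution condition: "this section (16) will be relevant in the rare case of any adverse event that is being reported retrospectively". The second covers new events and has one: "a rare event that occurs in the course of longer follow up that may be attributed to radiation therapy". Examples follow (lung and oesophageal cancer, angiosarcoma, ischaemic heart disease, rib fracture), and the list is left open.

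The recording rules inside the section are unconditional. Section 16.3: "All adverse events will be recorded in the CRF until the participant completes the study". Section 16.4: "All serious adverse events will be recorded in the medical records and the CRF". Appendix 1 (Schedule of assessments) marks an adverse event review at consent, at each annual direct contact and at the end of contact, again without a condition.

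The reporting rule is narrower. Section 16.4 requires an SAE form, sent to the Sponsor, for all SAEs "except those specified in section 16.5 as not requiring reporting to the Sponsor". Section 16.5 then states that "the only reportable adverse events are those that that occur in the course of longer follow up that may be attributed to radiation therapy", with the same open list.

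On judging the cause, section 16.2.2 says that the assessment of relationship "is a clinical decision based on all available information at the time of the completion of the case report form". No blinding is mentioned there. By contrast, section 5 (Work Package 1) has cause of death reviewed without knowledge of the allocated arm. The same section names complications and side effects among the secondary outcomes.

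**The concern.** The scope paragraph governs everything beneath it, including 16.3 and 16.4. Read literally, it takes a new late event that the site thinks unrelated to radiation out of the section, and so out of the rule that all events are recorded. Read alone, 16.3, 16.4 and Appendix 1 say the opposite. Two sites could follow the protocol in good faith and collect different data.

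What is at stake is the between-arm comparison of late complications. If entry in the CRF depends on attribution, the comparison counts attributed events rather than events. Attribution could differ by arm, because the treatments are plainly different to anyone who knows the patient: a single intraoperative dose against a daily course over weeks. An event never entered cannot be recovered by any analysis, so this has to be settled in the data-collection rules.

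**Working it through.** The protocol gives no figure to reproduce, so the check sets the sections side by side.

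1. **Does 16.5 by itself restrict recording?** No. Its heading concerns SAEs that need not be reported, and 16.4 cites it as an exemption from the SAE form and from reporting to the Sponsor. The same 16.4 puts all SAEs in the CRF. Recording everything while forwarding only some events is coherent.

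2. **Is 16.5 clearly drafted as that exemption?** Only in part. Its body speaks of adverse events, not SAEs, and names no recipient. The exempt events that 16.4 says are specified there are not listed. They are what remains after an attribution judgement over an open list.

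3. **Does the opening of section 16 restrict recording?** On its face, yes, for new events. It refers to the section as a whole, so its second limb reaches 16.3 and 16.4. The first limb (events reported retrospectively) is unfiltered.

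4. **Do other places resolve the conflict?** No. Appendix 1 supports the unconditional reading. Section 16.2.2 stresses the capture of treatment-related events and still contains a template drafting prompt, which suggests that the section was not fully adapted to this study.

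5. **Which events are exposed?** Section 3 collects other cancers and deaths, with cause, for all enrolled patients. Work Package 2 adds ONS deaths and new primary cancers for UK patients. Neither depends on attribution. That leaves non-fatal, non-cancer late events such as ischaemic heart disease and rib fracture. A patient questionnaire may flag one, but section 5 then refers the query to site staff, who work under section 16.

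6. **What would a filter do?** Suppose equal true risk in both arms, and let s1 (TARGIT) and s2 (whole-breast treatment) be the proportions of events kept. The observed risk ratio is then s1/s2. All values below are assumptions; the protocol gives none.
   - Equal filters: s1/s2 = 1, so no distortion.
   - 0.75/0.80 = 0.94 and 0.70/0.90 = 0.78.
   - The same pairs reversed: 0.80/0.75 = 1.07 and 0.90/0.70 = 1.29.

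The algebra shows only that a filter that differs by arm distorts the ratio. It applies only if attribution decides what enters the CRF.

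**The case against.** The strongest reply is that recording and reporting are different things. Section 16.5 governs reporting, while 16.3 and 16.4 keep every event in the CRF. Appendix 1 and the patient-completed questionnaires mean that capture does not start with a staff judgement. The phrase on attribution, followed by named conditions, can also be read as describing types of event that are the same in both arms. The original TARGIT-A protocol and the SAP, not available here, may define how complications are collected and compared.

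Much of this stands. A reader might infer that late events are kept only if staff who know the arm attribute them to radiation, and that late toxicity and mortality are therefore tilted towards TARGIT. The protocol does not support that:

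- 16.3 and 16.4, read alone, keep everything.
- Staff knowledge of the arm is a reasonable inference from the two treatments, but it is not stated.
- Cause of death is reviewed blinded, and deaths and new cancers are collected whatever their attribution.
- Nothing in the text shows that attribution would be more frequent in one arm.

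The reply does not remove the scope paragraph of section 16. That paragraph conditions the whole section, not just reporting, and nothing elsewhere says that 16.3 overrides it.

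**Conclusion.** The point holds as a contradiction in the rules for capturing late events, not as a demonstrated bias. The opening of section 16 conflicts with 16.3, 16.4 and Appendix 1 over new events that are not attributed to radiation, and the loose drafting of 16.5 reinforces the narrower reading.

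The exposure is limited to non-fatal, non-cancer late events and, through them, to the complications and side-effects secondary outcome. Any bias requires two things that the protocol does not establish: that sites apply the narrower rule when completing the CRF, and that their attribution judgements differ by arm. Its size and direction are therefore unknown. It is still worth correcting, because the loss could not be repaired at analysis and the remedy is cheap.

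**What to change.** Reconcile the opening of section 16 with 16.3, 16.4, 16.5 and Appendix 1 by stating three things:

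- Section 16.5 limits only the completion of the SAE form and reporting to the Sponsor.
- Recording of adverse events in the CRF does not depend on attribution, in either arm.
- Causality is a separate field and does not decide whether an event enters the between-arm comparison.

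The scope sentence of section 16 should be reworded so that it no longer conditions 16.3. Capture should not be restricted to a closed list: the named conditions are examples, and a fixed list could miss unexpected harms.

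The cost is a few sentences of protocol wording and a few more events recorded on forms already sent annually.

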16.6 Reporting Urgent Safety Measures

If any urgent safety measures are taken the CI/ PI shall immediately and in any event no later than 3 days from the date the measures are taken, give written notice to the relevant REC and Sponsor of the measures taken and the circumstances giving rise to those measures.

16.7 Protocol deviations and notification of protocol violations

A deviation is usually an unintended departure from the expected conduct of the study protocol/SOPs, which does not need to be reported to the sponsor. The CI will monitor protocol deviations.

A protocol violation is a breach which is likely to effect to a significant degree -

- (a) the safety or physical or mental integrity of the participants of the study; or
- (b) the scientific value of the study.

The CI and sponsor will be notified immediately of any case where the above definition applies during the study conduct phase.

16.8 Reporting incidents involving a medical device

Any adverse incident involving a medical device should be reported to the manufacturer of the device.

This is especially important where the incident has led to or, was it to occur again could lead to an event classified as serious (see section 9.1 for definition of SAE). Other minor safety or quality problems should be reported along with incidents that appear to be caused by human error.

All adverse incidents must be reported to Carl Zeiss, Oberkochen, Germany.

Incidents should be reported as soon as possible (usually within 24 hours).

Local trust reporting procedures may also need to be followed. It is the responsibility of the PI and study site team to ensure they are aware of any specific local requirements for reporting device incidents.

16.9 Trust incidents and near misses

An incident or near miss is any unintended or unexpected event that could have or did lead to harm, loss or damage that contains one or more of the following components:

- a. It is an accident or other incident which results in injury or ill health.
- b. It is contrary to specified or expected standard of patient care or service.
- c. It places patients, staff members, visitors, contractors or members of the public at unnecessary risk.
- d. It puts the Trust in an adverse position with potential loss of reputation.
- e. It puts Trust property or assets in an adverse position or at risk.

Incidents and near misses must be reported to the Trust through DATIX as soon as the individual becomes aware of them.

A reportable incident is any unintended or unexpected event that could have or did lead to harm, loss or damage that contains one or more of the following components:

Extended follow up of the TARGIT-A trial - Protocol

IRAS No: 236431

- a) It is an accident or other incident which results in injury or ill health.
- b) It is contrary to specified or expected standard of patient care or service.
- c) It places patients, staff members, visitors, contractors or members of the public at unnecessary risk.
- d) It puts the Trust in an adverse position with potential loss of reputation.
- e) It puts Trust property or assets in an adverse position or at risk of loss or damage.

